1.8.2 Statistical Modelling

An exploratory analysis will be performed, consisting of a multinomial logistic regression model that assesses the effect of patient characteristics and the site type on the outcome variable.

The previously defined outcome variable has four levels (chemo, IO, IO+chemo and BSC). The level with the highest frequency will be used as the reference in the multinomial logistic model.

Variables considered as predictors in the model are the site type and patient characteristics with less than 20% missing or unknown values. In case of yes/no variables with further conditional questioning (e.g. Inflammatory interstitial lung disease (yes/no) and if yes, Active/non-active) only the yes/no variable is included in the model. Selection of the final model, containing only predictors with a significant effect on the outcome variable, will be done using automatic selection procedures.

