2.1 Primary Objective(s) & Hypothesis(es)

The objective of this study is to investigate the relation between patient, tumor and site characteristics and systemic treatment choices of stage IV untreated NSCLC.

Systemic treatment choices and best supportive care are defined as :

- 1) Chemotherapy (chemo)
- 2) Immunotherapy (IO)
- 3) Immuno combined therapies (IO+IO)
- 4) IO+chemo
- 5) IO+bevacizumab+chemo (IO+bev+chemo)
- 6) Best supportive care (BSC).

It is hypothesized that there is a relation between the systemic treatment choice and the explanatory variable categories listed below. It is assumed that the variable categories have a different weight for the different systemic treatment options:

- Patient demography characteristics
- Medical history
- Co-morbidities
- Autoimmune disease
- Current/recent medication
- Prior cancer treatment in earlier stage
- Site characteristics

The details of the variables can be found in the section 4.2.

For each of the variable categories, it will be queried whether the variable category had an impact on the systemic treatment choice.

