9.1 Statistical Methods

The statistical analysis will be performed using SAS software 9.2.

9.1.1 Primary Objective(s): Calculation of Epidemiological Measure(s) of Interest (e.g. descriptive statistics, hazard ratios, incidence rates, test/retest reliability)

Systemic treatment choices and best supportive care are defined as :

- 1) Chemotherapy (chemo)
- 2) Immunotherapy (IO)
- 3) immuno combined therapies (IO+IO)
- 4) IO+chemo
- 5) IO+bevacizumab+chemo (IO+bev+chemo)
- 6) best supportive care (BSC).

Descriptive statistics of the relation between variable category and systemic treatment choice will be provided. The descriptive statistics will involve the number of times (frequency) a variable category is indicated as being linked to a systemic treatment option.

For each of the variable categories that are linked to a systemic treatment choice, descriptive statistics of the underlying variables will be provided. These descriptive statistics will consist of:

- For the quantitative variables, summary statistics including mean, standard deviation, 95% confidence interval on the mean, minimum, first quartile, median, third quartile, maximum, and number of available and number of missing observations.
- For the categorical variables, frequencies and percentages.

In an exploratory analysis, a penalized hierarchical logistic regression model for discrete choices will be used to evaluate the effect of the potential explanatory variables on the 1st line systemic treatment.

9.1.2 Secondary Objective(s): Calculation of Epidemiological Measure(s) of Interest (e.g. hazard ratios, incidence rates, test/retest reliability)

No secondary objectives.

9.1.3 Exploratory Objective(s): Calculation of Epidemiological Measure(s) of Interest (e.g. hazard ratios, incidence rates, test/retest reliability)

Investigate if there are differences in the link between variable categories and systemic treatment choices for the 4 types of sites that are defined.

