1.9 Deviations from the Analysis Foreseen in the Protocol

The protocol foresaw an exploratory analysis of the outcome variable using a penalized hierarchical logistic regression model for discrete choices.

Since a penalized logistic regression is not available in SAS, it was decided to use the classical multinomial logistic regression approach, with a stepwise selection procedure.

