2.5 Exploratory Analysis

The following variables will be considered in a multinomial stepwise logistic regression analysis:

- Site type (4 subgroups)
- Age
- Gender
- Weight loss
- Smoking status (current/former (≥ 1 year)/never)
- ECOG status (0/1/2/3-4)
- Patients' preference for treatment choice (yes/no)
- Metastatic disease status (M1a/M1b/M1c)
- Tumor size diameter
- Number of metastatic sites
- Brainmets (yes/no)
- Livermets (present/not present)
- Concomitant malignancies (present/not present)
- Histology (squamous/non-squamous)
- IHC PD-L1 (PD-L1 TPS $<1\%$ / $1-49\%$ / $\geq 50\%$)
- High TMB (present/not present)
- Genetic testing complications (turn-around time/biopsy availability)
- Each co-morbidity (yes/no)
- Each auto-immune disease (yes/no)
- Use of corticosteroids, other immunosuppressants, and antibiotics (yes/no)
- Use of each prior cancer treatment in earlier stage NSCLC (yes/no)

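### Site type, a hospital-level variable, is tested in the SAP as if each patient were an independent observation; any correlation left within hospitals makes that test reject too often

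*SAP*

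**What the plan says.** **Data structure.** Protocol 3.2 and 9.2.1 plan 210 patients in about 21 hospitals, at most 10% from any one. The outcome is the treating physician's choice. SAP 1.6 builds four site types from two hospital-level facts, diagnostic volume and participation in interventional trials.

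**Model.** SAP 1.8.2 describes "a multinomial logistic regression model that assesses the effect of patient characteristics and the site type on the outcome variable". SAP 2.5 states: "The following variables will be considered in a multinomial stepwise logistic regression analysis"; site type heads the list and hospital is not on it. On retention, SAP 1.8.2 says: "Selection of the final model, containing only predictors with a significant effect on the outcome variable". The significance level is not stated. Neither section mentions a random site effect, a clustered variance or a test with the hospital as unit.

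**Change from the protocol.** Protocol 9.1.1 says "a penalized hierarchical logistic regression model for discrete choices will be used to evaluate the effect of the potential explanatory variables". SAP 1.9 discloses the replacement and gives its reason: "Since a penalized logistic regression is not available in SAS, it was decided to use the classical multinomial logistic regression approach".

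**Role.** The objective in protocol 2.1 is to "investigate the relation between patient, tumor and site characteristics and systemic treatment choices of stage IV untreated NSCLC". The regression is labelled exploratory in both documents.

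**The concern.** A patient-level test compares the differences between site types with patient-to-patient variation. For a variable that is constant within a hospital, the right yardstick is hospital-to-hospital variation. Physicians in one hospital may share habits, tumour-board practice and access to testing. If such influences remain after the patient covariates are in the model, the test takes ordinary differences between hospitals as evidence about hospital types.

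At stake is what a reader concludes from a retained site type. Because the final model keeps only significant predictors, its presence there will be read as a finding about volume or trial participation. It could come from a few individual hospitals.

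**Working it through.** The documents state no power, significance level or ICC, so there is no plan figure to reproduce.

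**Inputs from the documents**
- 210 patients / 21 hospitals = 10 per hospital (protocol 3.2, 9.2.1).
- Four outcome levels (SAP 1.2.2) and four site types (SAP 1.6): (4 - 1) x (4 - 1) = 9 degrees of freedom.
- High volume means above the median (SAP 1.6), so with 21 distinct volumes 10 hospitals are high and 11 low.

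**Assumptions**
- 5% level, so the chi-square critical value on 9 df is 16.92.
- No true site-type effect.
- Layout 7/3 (high volume, with/without trials) and 7/4 (low volume).
- Outcome split 35/30/20/15% in the runs without covariates.
- Normal hospital effects with variance s² on each logit; latent ICC = s²/(s² + π²/3).

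**Step 1: approximation.** Design effect D = 1 + (10 - 1) x ICC, with ICC on the observed (0/1) scale. Rejection rate = P(χ²₉ > 16.92/D). Example at latent ICC 0.05: s² = (0.05/0.95) x 3.29 = 0.173. The observed-scale ICC is then 0.014-0.039, depending on the outcome category. At the upper end D = 1 + 9 x 0.039 = 1.351, 16.92/1.351 = 12.52, and P(χ²₉ > 12.52) = 18.5%.

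**Step 2: simulation of the 9-df test.** Hospitals of equal size, or of unequal size capped at 20 patients. The adjusted column is a score test with PD-L1, histology and ECOG in the model.

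| Latent ICC | Observed-scale ICC | D | Approximation | Simulated, no covariates | Simulated, adjusted |
|---|---|---|---|---|---|
| 0 | 0 | 1 | 5% | 4-6% | 5-7% |
| 0.02 | 0.006-0.016 | 1.05-1.14 | 7-10% | 7-10% | 10-11% |
| 0.05 | 0.014-0.039 | 1.13-1.35 | 9-19% | 13-18% | 13-16% |
| 0.10 | 0.029-0.077 | 1.26-1.69 | 15-35% | 26-33% | 23-27% |

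The scale matters. An ICC of 0.05 or 0.10 on the observed scale gives D = 1.45 or 1.90 and approximate rejection of 23% or 45%. These are larger degrees of clustering than the same latent values.

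**Step 3: when the problem goes away.** With hospitals differing only through case mix (latent 0.15) that is in the model, the test rejected 9-11% unadjusted and 5-7% adjusted.

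**Step 4: site size linked to site type.** This is plausible, since type is defined partly by volume. Without covariates, the patient-level test then rejected 11-13% at latent ICC 0.05 and 20-24% at 0.10.

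**Step 5: remedies.**
- Permuting site-type labels among the 21 hospitals rejected about 3-7% with or without the three covariates. With size linked to type it rejected 2.3-5.4%, which is valid but sometimes conservative.
- With covariates chosen by stepwise selection, the permutation test rejected 5.7-8.4%, so the covariate set should be fixed first.
- A site-clustered Wald test without covariates fails: even at ICC 0 it rejected 75-79% against chi-square and 26-30% against a Hotelling-type F. Site types with three or four hospitals are too few for it.
- A random site intercept was not simulated.

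**The case against.** **The size rests on an unknown.** This stands. Nothing in the documents places the residual ICC above 0.02, where the effect is small. What is certain is the omission; its consequence is conditional.

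**The model is exploratory.** Also true: the core results are descriptive, protocol 9.2.2 calls multiplicity adjustment not applicable, and no type I error control is claimed. Stepwise selection is loose in any case: in a simulation with 42 candidates it admitted about two null patient variables per run at every ICC. That run assumed prevalences and ignored the SAP's rule excluding variables with 20% or more missing values, so it does not reproduce the planned analysis. These facts lower the priority. They do not remove the point, because no other SAP analysis tests site characteristics and a better test is cheap.

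**The plan already guards against bias by site.** The 10% cap and consecutive inclusion limit selection and dominance by one hospital. They do not address correlation within hospitals.

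**Stronger readings that the documents do not support**
- A reader might infer that the SAP silently dropped a random site effect. SAP 1.9 discloses the replacement openly, and the protocol never defines *hierarchical*. Patients within hospitals is the natural reading, but the word could refer to variables within the protocol's variable categories; if the penalty was structured on those, the stated reason could cover both words. Only a clarification is due.
- A reader might infer that the exact 95% intervals are invalid. In simulation, the overall intervals covered 94-96% at latent ICC 0.01-0.02, 91-95% at 0.05 and 87-94% at 0.10. For descriptive intervals this is minor.
- A reader might infer that the exploratory objective in protocol 9.1.3 is undermined. That objective asks whether the link between variable categories and choice differs by site type; the site-type main effect does not address it either way.

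**Conclusion.** The point holds in conditional form. The SAP tests a hospital-level variable against patient-level variation and makes no allowance for hospital. If choices remain correlated within hospitals after adjustment, site type will be declared significant too often. Under the assumptions above, excess false significance is modest at latent ICC 0.02 and substantial at 0.05 to 0.10. It is absent if the modelled case mix accounts for the hospital differences. The documents do not show which case applies, so no particular error rate can be attributed to this study. Because the model is exploratory, this is a cheap improvement and not a threat to the primary descriptive results.

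**What to change.** 1. **SAP 1.8.2 and 2.5.** Take site type out of the stepwise selection and judge it against between-hospital variation. One option is to permute site-type labels among hospitals, with a covariate set fixed before that test is run. Another is a random site intercept, if it converges; its feasibility in SAS 9.2 was not checked. Otherwise report site type descriptively only. Do not call it significant from the patient-level test, and do not use a site-clustered Wald test when a type has only three or four hospitals.
2. **SAP 2.3 (minor).** Show the number of hospitals behind each site-type interval, and state that the exact 95% intervals do not allow for clustering. The 30-patient subgroup minimum in protocol 9.3 does not cover this: three hospitals of ten patients meet it.
3. **SAP 1.9 (minor).** Say what *hierarchical* meant in the protocol and, if it meant site, what replaces it. The stated reason mentions penalisation only.

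**Cost.** SAP wording and modest programming. No new data are needed, since SAP 2.1 already tabulates by site. With about 21 hospitals a valid site-level test has limited power, and permutation may be conservative if site size is linked to site type.

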1.4 Sample Size Justification

No formal sample size calculation was performed. The protocol states that a maximum of 210 eligible patients and a minimum of 200 patients are to be included to have a representative picture of the pneumo-oncologists' NSCLC systemic treatment decision in Belgium.

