1.5.2 Patient Characteristics

After making the treatment choice, the investigator records the following variables and indicates whether the characteristic impacted the treatment choice (yes/no). Of the variables indicated as having an impact, the investigator chooses at least one and a maximum of three most important characteristics.

Demographic data

- Age (years)
- Gender (male/female)
- Weight loss (%)
- Smoking status (current/former (≥ 1 year)/never/unknown¹)
- ECOG status (0/1/2/3-4/unknown¹)
- Patients' preference for treatment choice (yes/no/unknown¹)

Medical history

- Metastatic disease status (M1a/M1b/M1c/unknown¹)
- Tumor burden:
 - Tumor size diameter (mm)
 - Number of metastatic sites
- Brainmets (yes/no), if yes:
 - Symptomatic/asymptomatic
 - Treated with SRT/treated with WBRT/not treated
- Livermets (present/not present/unknown¹)
- Concomitant malignancies (present/not present/unknown¹)
- Histology (squamous/non-squamous/not otherwise specified¹)
- IHC PD-L1 (PD-L1 TPS $< 1\%$ / $1-49\%$ / $\geq 50\%$ / unknown¹)
- High TMB (≥ 10 mutations/Mb) (present/not present/unknown¹)
- Genetic testing complications (turnaround time/biopsy availability/not tested¹/not applicable¹)

Co-morbidities

Presence (yes/no) of the following diseases:

- Myocardial infarction in the last year
- Congestive heart failure
- Peripheral vascular disease
- Hypertension
- Cerebrovascular event in the last year
- Transient ischemic attack in the last year
- Diabetes with complications
- Renal disease
- Liver disease
- Hematological disease
- Chronic obstructive pulmonary disease
- Chronic infections
- Mental disorders

¹ Considered missing in the analysis

Autoimmune disease

Presence, and in case present, active (yes/no), of the following diseases:

- Inflammatory interstitial lung disease
- Inflammatory bowel disease (IBD)
- Inflammatory joint disease
- Psoriasis
- Connective tissue disease

Current/recent medication

- Corticosteroids (yes/no), and if yes, low dose/high dose (≥ 10 mg/day Prednisolone or equivalent)
- Other immunosuppressants
- Antibiotics

Prior cancer treatment in earlier stage NSCLC

Did the patient undergo the following treatment (yes/no) and if yes, the year of the treatment:

- Single-modality treatment
- Multi-modality treatment
- Surgery/radiotherapy
- Previous IO treatment

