1.7 Analysis Set

The following analysis set is considered:

Eligible Population (EP): All subjects enrolled in the study, who have given informed consent and who satisfied all inclusion and none of the exclusion criteria.

The patients that should be excluded from the EP will be discussed during a data review meeting.

All analyses will be performed on the EP.

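### The model's 20% missing-data screen works one variable at a time, so the stepwise model would probably be fitted only on patients complete on every candidate offered, including candidates later discarded

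*SAP*

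**What the plan says.** SAP 1.8.2 has one missing-data rule for the model: "Variables considered as predictors in the model are the site type and patient characteristics with less than 20% missing or unknown values". The percentage is judged for each variable separately and over all patients together.

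SAP 1.5.2 marks several codes with a footnote, "Considered missing in the analysis". Besides plain unknowns, these include a recorded diagnosis, "Histology (squamous/non-squamous/not otherwise specified¹", and the absence of a test, "Genetic testing complications (turnaround time/biopsy availability/not tested¹/not applicable¹".

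SAP 2.5 opens its candidate list with "The following variables will be considered in a multinomial stepwise logistic regression analysis". The levels it shows have no category for unknown, and it does not repeat the 20% condition.

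On the method, SAP 1.9 says "it was decided to use the classical multinomial logistic regression approach, with a stepwise selection procedure". On numbers, SAP 1.4 says "a maximum of 210 eligible patients and a minimum of 200 patients are to be included". SAP 1.7 adds "All analyses will be performed on the EP", where EP is the eligible population.

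Neither document gives an imputation method, a limit on joint missingness, a check within treatment choices, a minimum number of complete patients, or a rule on which patients the final model is fitted to.

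**The concern.** A limit on each variable does not limit what happens when many variables are used together. A classical logistic regression needs a value for every variable it is given. With stepwise selection in SAS, the usual behaviour is to fix the patient set at the start, from all variables offered. A patient with an unknown liver-metastasis status would then be lost to the whole analysis even if liver metastasis never enters the model.

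Two things are at stake. The first is precision: the fit may rest on clearly fewer than the 200 to 210 patients, and nothing requires the modelled number to be shown. The second is validity. The screen pools treatment choices, so it can pass a variable that is largely missing in one small group, such as best supportive care (BSC). If missingness also varies with a predictor inside that group, the odds ratios for that group are distorted. This is the only multivariable analysis of the relation that the primary objective names, so readers may take its odds ratios as describing the whole eligible population.

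**Working it through.** The documents state no missing-data rate, complete-patient count or BSC count, so there is no figure of the plan's own to reproduce. All missing rates below are assumptions.

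**Candidates.** SAP 2.5 lists 17 single items, 13 co-morbidities, 5 autoimmune diseases, 3 medications and 4 prior treatments: 17 + 13 + 5 + 3 + 4 = 42. Ten carry a code treated as missing: smoking, ECOG, preference, metastatic status, liver metastases, concomitant malignancies, histology, PD-L1, TMB and genetic testing complications. Weight loss, tumor size and number of metastatic sites can be blank, which makes 13. TMB and genetic testing complications may well fail the 20% screen, so 10 incomplete candidates is a reasonable working number.

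**Joint loss.** Let N = 210, with k = 10 candidates each missing in a share m.

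- Independent gaps: N(1 − m)^k
- Gaps all in the same patients: N(1 − m)
- Gaps never in the same patient: N(1 − km), not below 0

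| m | Independent | Same patients | Never overlapping |
|---|---|---|---|
| 2% | 210 × 0.817 = 172 | 206 (98%) | 168 |
| 5% | 210 × 0.599 = 126 | 200 (95%) | 105 |
| 10% | 210 × 0.349 = 73 | 189 (90%) | 0 |

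Every m in the table passes the screen. Under independence, fewer than half of the patients remain once m exceeds 1 − 0.5^(1/10) = 6.7%.

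**Loss to discarded candidates.** Suppose 3 of the 10 are retained. A refit on patients complete on those 3 would use 210 × 0.98^3 = 198, 210 × 0.95^3 = 180 or 210 × 0.90^3 = 153 patients, against 172, 126 or 73.

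**Loss within a treatment choice.** The largest missing count that passes is 41 of 210 (41/210 = 19.5%; 42/210 = 20.0% fails), or 39 of 200. A group of 41 or fewer could therefore be entirely missing on a variable that is kept.

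- Extreme case: 30 BSC patients, all missing on one variable, plus 5% of the other 180. That is (30 + 9)/210 = 18.6%, so the variable passes and no BSC patient remains.
- Milder case: 30 BSC patients, 5 variables, 20% missing in BSC and 5% elsewhere, that is (6 + 9)/210 = 7.1% per variable. This leaves 30 × 0.8^5 = 9.8 BSC and 180 × 0.95^5 = 139.3 others. The BSC share falls from 14.3% to 9.8/149.1 = 6.6%.
- Equal missingness in all groups: the BSC share stays at 14.3%.

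**Bias.** In a complete-patient fit, the odds ratio for a binary predictor is multiplied by (r11 × r00)/(r10 × r01), where r is the share kept, the first index is the treatment choice (1 = BSC, 0 = reference) and the second is the predictor. If r depends on treatment choice alone, or on the predictor alone, the factor is 1. If r is 0.30 for BSC patients with ECOG 2 or more, 0.70 for other BSC patients, and equal across ECOG in the reference group, the factor is 0.30/0.70 = 0.43. These rates are illustrative only.

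**The case against.** The strongest reply is that much of this is inference. The SAP never says complete cases. It speaks of selecting a final model, and nothing forbids fitting that model to everyone with data on its predictors. That stands: the complete-patient fit is deduced from the missing codes, the classical model, the software and the silence on handling. But nothing in the plan leads the programmer to do otherwise.

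Secondly, 42 candidates overstates the exposure. The 25 co-morbidity, autoimmune, medication and prior-treatment items have no unknown code, and the least complete variables may be screened out. This also stands, and is why the working uses 10 candidates.

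Thirdly, the size is unknown. With 2% missing on each of 10 variables, 172 to 206 patients remain between independence and full overlap, a modest loss. A reader might infer that the model will rest on a minority of patients; no missing rate in the documents supports that.

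Fourthly, a reader might infer that SAP 1.7 is contradicted. It is not clearly so. The eligible population is defined by consent and eligibility, not by complete covariates, and SAP 1.8.1 itself counts missing observations within analyses of that population.

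Fifthly, a reader might infer that BSC patients are tested less and that the odds ratios are therefore biased. Neither document reports missingness by treatment choice, and bias needs joint dependence on treatment choice and a predictor. What remains is that the screen could not detect this if it occurred.

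**Conclusion.** The point holds as a gap in the exploratory model. The screen controls missingness per variable only, and the likely consequence is a fit restricted to patients complete on every candidate that passes, including those later discarded. This rests on the standard behaviour of SAS stepwise logistic regression, not on a statement in the SAP.

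The size cannot be fixed from the documents: under the assumptions shown, 73 to 172 of 210 patients remain with independent gaps and 189 to 206 with full overlap. What needs no assumed rate is that 41 missing of 210 passes the rule, so a treatment choice of that size or smaller is unprotected. Bias is conditional on joint dependence that is plausible but undocumented.

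The descriptive analysis, which carries the primary objective, is unaffected, and the model is labelled exploratory. This is a cheap, worthwhile improvement and does not invalidate the plan.

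**What to change.** In SAP 1.8.2:

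1. After selection, refit the final model on all eligible patients complete on the retained predictors, and report that fit.
2. Report the modelled number per treatment choice beside the number in the eligible population.
3. Add a sensitivity analysis by multiple imputation, with treatment choice and site in the imputation model. The refit recovers patients lost to discarded candidates but cannot correct loss from a retained variable such as PD-L1.
4. Tabulate missingness of each candidate by treatment choice as a flag. Do not make it an exclusion rule: a 20% limit within each treatment choice could remove PD-L1, which Protocol 1.1 names as a basis of first-line decisions.

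Also state in SAP 2.5 that its list is subject to the 20% condition of 1.8.2.

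The cost is SAP wording and a few hours of programming. The downside is that selection and the final fit use different patient sets, which the report must state.
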